**Table 10: Subjects Who Discontinue Study Treatment but Remain in the Study – Placebo-Controlled Period**

Study Week	Placebo-Controlled Period 							UV for ARIA 
	12	24	26	48	50	72	78 (EOT) 	
Study Day	85 ± 3	169 ± 3	183 ± 3	337 ± 3	351 ± 3	505 ± 3	547 ± 3	
Informed Consent							X 	
Body Weight	X	X		X		X		
Eligibility Criteria							X 	
Physical Examination	X	X		X		X	X	
Neurological Examination	X	X		X		X	X	
12-lead Paper ECG		X		X		X	X	
Vital Signs	X	X		X		X		
Hematology, Blood Chemistry and Urinalysis		X		X		X	X	
PBMC Collection								X 
Aducanumab Concentration								X 
Brain MRI 							X	X
Amyloid PET 			X				X	
CDR			X		X		X	
MMSE			X		X		X	
ADAS-Cog 13			X		X		X	
ADCS-ADL-MCT			X		X		X	

CONFIDENTIAL

The information contained herein may not be used, disclosed, or published without the written consent of Biogen MA Inc.

Study Week	Placebo-Controlled Period 							UV for ARIA 
	12	24	26	48	50	72	78 (EOT) 	
Study Day	85 ± 3	169 ± 3	183 ± 3	337 ± 3	351 ± 3	505 ± 3	547 ± 3	
NPI-10			X		X		X	
EQ-5D (SR)			X		X		X	
EQ-5D (IR-S)			X		X		X	
[REDACTED]								
mPDQ-20			X		X		X	
[REDACTED]								
MOCA								X
C-SSRS			X				X	
AE Reporting	Monitor and record continuously throughout the study							
Concomitant Therapy and Procedures	Monitor and record continuously throughout the study							
SAE Reporting	Monitor and record continuously throughout the study							

AD = Alzheimer's disease; AE = adverse event; ADAS-Cog 13 = Alzheimer's Disease Assessment Scale Cognitive Subscale (13 items); ADCS-ADL-MCI = Alzheimer's Disease Cooperative Study Activities of Daily Living Inventory (Mild Cognitive Impairment version); ARIA = amyloid-related imaging abnormalities; ARIA-E = amyloid-related imaging abnormality-edema; ARIA-H = amyloid-related imaging abnormality hemorrhage or superficial siderosis; [REDACTED] CDR = Clinical Dementia Rating scale; [REDACTED]; C-SSRS = Columbia Suicide Severity Rating Scale; ECG = electrocardiogram; EOT = end of treatment; [REDACTED]; EQ-5D (IR-S) = EQ-5D, informant reported on subject; EQ-5D (SR) = EQ-5D, subject self-reported; FU = follow-up; LTE = long-term extension; MMSE = Mini Mental State Examination; mPDQ-20 = modified Perceived Deficits Questionnaire-20; MOCA = Montreal Cognitive Assessment; MRI = magnetic resonance imaging; NPI-10 = Neuropsychiatric Inventory-10; PBMC = peripheral blood mononuclear cells; PET = positron emission tomography; PK = pharmacokinetic; [REDACTED]; SAE = serious adverse event; SoE = schedule of events; UV = unscheduled visit.

 Subjects who discontinue study treatment prematurely during the placebo-controlled period are to remain in the study, attend a FU Visit 18 weeks after their final dose as listed in Table 2 and Table 3, and immediately continue protocol-required tests and assessments at a subset of the clinic visits (see Table 10, and Table 11) until the end of the study per the schedule of events. (It is possible that a clinic visit will occur before the FU Visit.) If the FU Visit will occur within 2 weeks of a scheduled clinic visit, then the FU Visit can be combined with the scheduled visit and all assessments required for both visits performed at this single visit. If the subject who discontinued treatment but remained in the study chooses to enroll in the LTE period, he or she will follow the SoE in Table 11.

CONFIDENTIAL

The information contained herein may not be used, disclosed, or published without the written consent of Biogen MA Inc.

-  Subjects who withdraw from study prematurely are to return to the site for an EOT Visit; for such subjects, efficacy assessments specified at the EOT Visit are not required if the subject discontinues treatment within 3 months of the previous efficacy assessment visit and no significant changes in cognitive status are suspected by the Investigator. The site should notify the Sponsor in such cases.
-  For the frequency of required brain MRI and MOCA assessments, and PK, biomarker, and PBMC sample collection for subjects who develop ARIA-E and/or ARIA-H, see Section 7.2.1.1 to Section 7.2.1.5. This includes PK, biomarker, and PBMC sample collection at the first unscheduled visit for ARIA monitoring per episode only. For the frequency of brain MRI and MOCA assessments following resolution of ARIA and resumption of dosing, see Section 7.2.1.6. For management of recurrent ARIA, see Section 7.2.1.7.
-  Only for subjects entering the long-term extension period.
-  Sample may be collected within  $\pm 2$  days of the MRI visit at the same time as sample collection for aducanumab concentration.
-  One sample will be collected within  $\pm 2$  days of the MRI visit. Exact collection date and time will be captured for all PK blood samples on a specified case report form.
-  Arterial spin labeling MRI and task-free functional MRI will be performed only at a subset of sites.
-  Only for subjects who participate in the amyloid PET substudy. Amyloid PET may be scheduled within a window of  $\pm 7$  days.

CONFIDENTIAL

The information contained herein may not be used, disclosed, or published without the written consent of Biogen MA Inc.

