**Table 2: Placebo-Controlled Period Schedule From Week 50 to End of Treatment or Follow-Up**

Study Week											FU 
	50	52	56	60	64	68	72	76	78 (EOT) 	UV for a Change in AD Medication	94 (or 18 wks after final dose for subjects who DCT early)
Study Day	351 ± 3	365 ± 3	393 ± 3	421 ± 3	449 ± 3	477 ± 3	505 ± 3	533 ± 3	547 ± 3		659 ± 7
Informed Consent									X 		
Eligibility Criteria									X 		
Body Weight		X	X	X	X	X	X	X			X
Urine Pregnancy Test 		X	X	X	X	X	X	X			X
Physical Examination							X		X		X
Neurological Examination							X		X		X
12-lead Paper ECG							X		X		X
Vital Signs 		X	X	X	X	X	X	X			X
Hematology, Blood Chemistry and Urinalysis							X		X		X
Study Treatment Infusion		X	X	X	X	X	X	X			

CONFIDENTIAL

The information contained herein may not be used, disclosed, or published without the written consent of Biogen MA Inc.

Study Week											FU 
	50	52	56	60	64	68	72	76	78 (EOT) 	UV for a Change in AD Medication	94 (or 18 wks after final dose for subjects who DCT early)
Study Day	351 ± 3	365 ± 3	393 ± 3	421 ± 3	449 ± 3	477 ± 3	505 ± 3	533 ± 3	547 ± 3		659 ± 7
Anti-Aducanumab Ab 			X						X		X
Aducanumab Concentration 		X 	X						X		X
PBMC Collection			X						X		X
Amyloid PET 									X		
CDR	X								X	X	X
MMSE	X								X	X	X
ADCS-ADL MCI	X								X	X	X
ADAS-Cog 13	X								X	X	X
NPI-10	X								X		
EQ-5D (SR)	X								X		

CONFIDENTIAL

The information contained herein may not be used, disclosed, or published without the written consent of Biogen MA Inc.

Study Week											FU 
	50	52	56	60	64	68	72	76	78 (EOT) 	UV for a Change in AD Medication	94 (or 18 wks after final dose for subjects who DCT early)
Study Day	351 ± 3	365 ± 3	393 ± 3	421 ± 3	449 ± 3	477 ± 3	505 ± 3	533 ± 3	547 ± 3		659 ± 7
EQ-5D (IR-S)	X								X		
mPDQ-20	X								X		
C-SSRS		X							X		
AE Reporting	Monitor and record continuously throughout the study										
Concomitant Therapy and Procedures	Monitor and record continuously throughout the study										
SAE Reporting	Monitor and record continuously throughout the study										

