**Table 11: Subjects Who Discontinue Study Treatment but Remain in the Study – Long-Term Extension Period**

Study Week	LTE Period 															UV for ARIA 
	92	104	106	128	134	152	162	176	182	208	232	260	284	312	338 (EOT) 	
Study Day	645 ± 5	729 ± 5	743 ± 5	897 ± 5	939 ± 5	1065 ± 5	1135 ± 5	1233 ± 5	1275 ± 5	1457 ± 5	1625 ± 5	1821 ± 5	1989 ± 5	2185 ± 5	2367 ± 5	
Body Weight	X	X		X		X		X	X	X	X	X	X	X	X	
Physical Examination	X	X		X		X		X	X	X	X	X	X	X	X	
Neurological Examination	X	X		X		X		X	X	X	X	X	X	X	X	
12-lead Paper ECG		X		X		X		X								
Vital Signs	X	X		X		X		X	X	X	X	X	X	X	X	
Hematology, Blood Chemistry and Urinalysis		X		X		X		X			X		X			
PBMC Collection																X 
Aducanumab Concentration																X 
Brain MRI 					X				X		X		X		X 	X
Amyloid PET 									X			X			X	
CDR			X		X		X		X		X		X		X	
MMSE			X		X		X		X		X		X		X	
ADAS-Cog 13			X		X		X		X		X		X		X	
ADCS-ADL-MCI			X		X		X		X		X		X		X	
NPI-10			X		X		X		X						X 	

CONFIDENTIAL

The information contained herein may not be used, disclosed, or published without the written consent of Biogen MA Inc.

Study Week	LTE Period 															UV for ARIA 
	92	104	106	128	134	152	162	176	182	208	232	260	284	312	338 (EOT) 	
Study Day	645 ± 5	729 ± 5	743 ± 5	897 ± 5	939 ± 5	1065 ± 5	1135 ± 5	1233 ± 5	1275 ± 5	1457 ± 5	1625 ± 5	1821 ± 5	1989 ± 5	2185 ± 5	2367 ± 5	
EQ-5D-(IR-S)			X		X		X		X		X		X		X	
MOCA																X
C-SSRS			X		X		X		X		X		X		X	
AE Reporting	Monitor and record continuously throughout the study															
Concomitant Therapy and Procedures	Monitor and record continuously throughout the study															
SAE Reporting	Monitor and record continuously throughout the study															

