### **16.5.2.5. Columbia Suicide Severity Rating Scale**

The C-SSRS data will be summarized by treatment group.

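### Subjects who permanently stop treatment before Week 52 but stay in the placebo-controlled period lose the mid-study C-SSRS, because Table 10 drops the Week 52 visit and does not carry the scale to Week 50

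*Protocol*

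**What the plan says.** All references are to protocol version 6.0, Section 4.2 unless stated otherwise.

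- **On treatment.** Table 1 places the C-SSRS on Day 1 and at Week 26. Table 2 ("Placebo-Controlled Period Schedule From Week 50 to End of Treatment or Follow-Up") places it at Weeks 52 and 78. In the same table CDR, MMSE, ADAS-Cog 13, ADCS-ADL-MCI, NPI-10, both EQ-5D forms and mPDQ-20 are at Week 50. Week 52 is the first of the seven infusion visits in Table 2 ("Study Treatment Infusion X X X X X X X"); there is no infusion at Week 50.
- **Off treatment, still in the study.** Table 10 ("Subjects Who Discontinue Study Treatment but Remain in the Study – Placebo-Controlled Period") lists Weeks "12 24 26 48 50 72 78 (EOT"). There is no Week 52. The scales named above are kept at Weeks 26, 50 and 78, while the C-SSRS is marked at Weeks 26 and 78 and its Week 50 cell is empty.
- **Extra visit.** A footnote to Table 10 has these subjects "attend a FU Visit 18 weeks after their final dose as listed in Table 2 and Table 3". The follow-up column of Table 2 has no C-SSRS, and Table 3 has no C-SSRS row.
- **Extension.** Table 11 ("Subjects Who Discontinue Study Treatment but Remain in the Study – Long-Term Extension Period") has seven C-SSRS marks ("C-SSRS X X X X X X X"), at Weeks 106, 134, 162, 182, 232, 284 and 338. These are the weeks used for treated subjects in Tables 4, 5, 7, 8 and 9.
- **Use.** Section 14.1 lists the C-SSRS among the clinical safety assessments. Section 16.5.2.5 states: "The C-SSRS data will be summarized by treatment group".

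**The concern.** A reduced schedule after stopping treatment is a legitimate choice. What looks unintended is that the single scale missing from an otherwise complete Week 50 assessment is a safety scale, and that the protocol gives no reason for it. The apparent cause is placement. The C-SSRS is at the same visit as the CDR everywhere in the study except Week 52, and Week 52 is the only C-SSRS time point that subjects off treatment lose.

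At stake is comparability of a safety summary. The C-SSRS is tabulated by arm. Section 10.1 makes certain ARIA events grounds for mandatory discontinuation, and Section 5.1.2 reports ARIA as dose-dependent in the earlier multiple-dose study. Permanent discontinuation may therefore differ between arms. If it does, the number of scheduled C-SSRS assessments per subject will differ between arms as well.

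**Working it through.** The protocol states no figure to reproduce here. The check is a reading of table cells followed by subtraction of nominal study days.

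**1. Inputs.** Nominal days from Tables 1, 2 and 10: Week 26 = Day 183, Week 50 = Day 351, Week 52 = Day 365, Week 78 = Day 547.

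**2. Scheduled post-baseline C-SSRS in the placebo-controlled period.**

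| Visit | On treatment (Tables 1, 2) | Off treatment (Table 10) |
|---|---|---|
| Week 26 | yes | yes |
| Week 50 | no (other scales only) | no (other scales only) |
| Week 52 | yes | visit not retained |
| Week 78 | yes | yes |
| Follow-up visit, 18 weeks after last dose | no | no |
| Total | 3 | 2 |

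One of three is lost: 1/3 = 33%.

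**3. Longest interval between scheduled assessments.**

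- On treatment: 365 − 183 = 182 days and 547 − 365 = 182 days (26 weeks each).
- Permanently off treatment before Week 52: 547 − 183 = 364 days (52 weeks).
- Ratio: 364 / 182 = 2.

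**4. Is Week 52 the odd one out?** The post-baseline C-SSRS weeks over the whole study are 26, 52, 78, 106, 134, 162, 182, 232, 284 and 338, ten in all. The CDR is scheduled at nine of them, all but Week 52. Infusion visits as such are not the cause: Weeks 232 and 284 are infusion visits, carry both scales, and are kept in Table 11.

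**5. Who is affected.** Three conditions must hold together: permanent discontinuation, before the Week 52 visit, with the subject remaining in the study. The following are not affected:

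- subjects who stop at or after Week 52, who have already had that C-SSRS;
- subjects suspended for ARIA, who under Section 7.2.1 continue to attend all scheduled visits and so keep Week 52;
- subjects who withdraw from the study, who return for an end-of-treatment visit. That column of Table 2 includes the C-SSRS, and the three-month waiver covers efficacy assessments only.

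**6. With a C-SSRS at Week 50 in Table 10.** 351 − 183 = 168 days and 547 − 351 = 196 days. The longest interval becomes 196 days, against 182 on treatment.

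**The case against.** The strongest reply is that nothing is contradicted. Table 10 is expressly a reduced set of visits, and other safety items shrink too: brain MRI goes from seven post-baseline time points in Table 3 (Weeks 14, 22, 30, 42, 54, 66 and 78) to Week 78 plus any ARIA visits. This stands as far as it goes. Tables 2 and 10 can both be followed as written. It explains why the Week 52 visit was dropped, but not why this scale alone was left out of Week 50. That the omission follows from placement is an inference from the pattern of the tables; the text does not say so.

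A reader might infer that suicidality will be under-ascertained in the arm with more discontinuations. The documents do not support that. Adverse event and serious adverse event reporting continues throughout Table 10, and these subjects are still seen at the retained visits and at the follow-up visit. The protocol does not give the recall period of the C-SSRS, so the Week 78 assessment may cover part or all of the gap. Nor does it give discontinuation rates by arm. Under-ascertainment is possible, not shown.

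A reader might also infer that everyone who stops treatment has the 52-week gap. The exclusions in step 5 rule that out.

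Last, for subjects who stop well before Week 52, drug exposure will largely have ended by then: Section 7.1 gives a mean half-life of about 20 days. This lowers the safety value of the lost assessment for early stoppers, but not for those who stop shortly before Week 52.

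**Conclusion.** The point holds within a narrow scope. In the placebo-controlled period, subjects who permanently discontinue before Week 52 and remain in the study lose one of three post-baseline C-SSRS assessments, and their longest nominal interval doubles from 182 to 364 days. The extension has no such loss.

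These figures rest only on the table cells and nominal study days. The number of subjects affected cannot be derived from the protocol. The 30% drop-out in Section 16.8 belongs to the Week 78 power calculation; it is not a rate of permanent discontinuation before Week 52 among subjects who stay.

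The consequence for the summary by arm is conditional: scheduled ascertainment differs between arms only if discontinuation does. This is a minor flaw in a safety schedule. It does not touch the primary analysis, and it is worth correcting because correction is nearly free.

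**What to change.** Add one C-SSRS mark at Week 50 in Table 10 and leave Week 52 in Table 2 unchanged. Subjects off treatment then have the C-SSRS at Weeks 26, 50 and 78, three assessments as on treatment, with a longest nominal gap of 196 days.

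The cost is one short questionnaire at a visit these subjects already attend for the other scales, and a two-week offset from the treated subjects' mid-study time point, which the summary should allow for by grouping Weeks 50 and 52. A subject who attends Week 50 on treatment and then permanently stops before Week 52 would still miss the assessment; a footnote to Table 10 can cover that case.

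Moving the C-SSRS to Week 50 for treated subjects as well is not needed. It would lengthen their last interval from 182 to 196 days and, with the trial under way, leave a mixture of Week 50 and Week 52 assessments among subjects on treatment.

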**Table 11: Subjects Who Discontinue Study Treatment but Remain in the Study – Long-Term Extension Period**

Study Week	LTE Period 															UV for ARIA 
	92	104	106	128	134	152	162	176	182	208	232	260	284	312	338 (EOT) 	
Study Day	645 ± 5	729 ± 5	743 ± 5	897 ± 5	939 ± 5	1065 ± 5	1135 ± 5	1233 ± 5	1275 ± 5	1457 ± 5	1625 ± 5	1821 ± 5	1989 ± 5	2185 ± 5	2367 ± 5	
Body Weight	X	X		X		X		X	X	X	X	X	X	X	X	
Physical Examination	X	X		X		X		X	X	X	X	X	X	X	X	
Neurological Examination	X	X		X		X		X	X	X	X	X	X	X	X	
12-lead Paper ECG		X		X		X		X								
Vital Signs	X	X		X		X		X	X	X	X	X	X	X	X	
Hematology, Blood Chemistry and Urinalysis		X		X		X		X			X		X			
PBMC Collection																X 
Aducanumab Concentration																X 
Brain MRI 					X				X		X		X		X 	X
Amyloid PET 									X			X			X	
CDR			X		X		X		X		X		X		X	
MMSE			X		X		X		X		X		X		X	
ADAS-Cog 13			X		X		X		X		X		X		X	
ADCS-ADL-MCI			X		X		X		X		X		X		X	
NPI-10			X		X		X		X						X 	

CONFIDENTIAL

The information contained herein may not be used, disclosed, or published without the written consent of Biogen MA Inc.

Study Week	LTE Period 															UV for ARIA 
	92	104	106	128	134	152	162	176	182	208	232	260	284	312	338 (EOT) 	
Study Day	645 ± 5	729 ± 5	743 ± 5	897 ± 5	939 ± 5	1065 ± 5	1135 ± 5	1233 ± 5	1275 ± 5	1457 ± 5	1625 ± 5	1821 ± 5	1989 ± 5	2185 ± 5	2367 ± 5	
EQ-5D-(IR-S)			X		X		X		X		X		X		X	
MOCA																X
C-SSRS			X		X		X		X		X		X		X	
AE Reporting	Monitor and record continuously throughout the study															
Concomitant Therapy and Procedures	Monitor and record continuously throughout the study															
SAE Reporting	Monitor and record continuously throughout the study															

AD = Alzheimer's disease; AE = adverse event; ADAS-Cog 13 = Alzheimer's Disease Assessment Scale Cognitive Subscale (13 items); ADCS-ADL-MCI = Alzheimer's Disease Cooperative Study Activities of Daily Living Inventory (Mild Cognitive Impairment version); ARIA = amyloid-related imaging abnormalities; ARIA-E = amyloid-related imaging abnormality-edema; ARIA-H = amyloid-related imaging abnormality hemorrhage or superficial siderosis; [REDACTED]; CDR = Clinical Dementia Rating scale; [REDACTED]; C-SSRS = Columbia Suicide Severity Rating Scale; ECG = electrocardiogram; EOT = end of treatment; [REDACTED]; EQ-5D (IR-S) = EQ-5D, informant reported on subject; FU = follow-up; LTE = long-term extension; MMSE = Mini Mental State Examination; MOCA = Montreal Cognitive Assessment; MRI = magnetic resonance imaging; NPI 10 = Neuropsychiatric Inventory-10; PBMC = peripheral blood mononuclear cells; PET = positron emission tomography; PK = pharmacokinetic; [REDACTED]; SAE = serious adverse event; UV = unscheduled visit.

-  Subjects who discontinue study treatment during the LTE period are to remain in the study, attend a FU Visit as listed in Table 9, and then will continue protocol-required tests and assessments at a subset of the clinic visits.
-  Subjects who withdraw from study prematurely are to return to the site for an EOT Visit; for such subjects, efficacy assessments specified at the EOT Visit are not required if the subject discontinues treatment within 3 months of the previous efficacy assessment visit and no significant changes in cognitive status are suspected by the Investigator. The site should notify the Sponsor in such cases.
-  For the frequency of required brain MRI and MOCA assessments, and PK, biomarker, and PBMC sample collection for subjects who develop ARIA-E and/or ARIA-H, see Section 7.2.1.1 to Section 7.2.1.5. This includes PK, biomarker, and PBMC sample collection at the first unscheduled visit for ARIA monitoring per episode only. For the frequency of brain MRI and MOCA assessments following resolution of ARIA and resumption of dosing, see Section 7.2.1.6. For management of recurrent ARIA, see Section 7.2.1.7.
-  This assessment is only to be performed if the EOT Visit is at or before Week 182.
-  Sample may be collected within ±2 days of the MRI visit at the same time as sample collection for aducanumab concentration.

CONFIDENTIAL

The information contained herein may not be used, disclosed, or published without the written consent of Biogen MA Inc.

-  One sample will be collected within  $\pm 2$  days of the MRI visit. Exact collection date and time will be captured for all PK blood samples on a specified case report form.
-  Arterial-spin labeling MRI and task-free functional MRI will be performed only at a subset of sites, and will not be performed at any visit after Week 182.
-  Only for subjects who participate in the amyloid PET substudy. Amyloid PET may be scheduled within a window of  $\pm 7$  days.

CONFIDENTIAL

The information contained herein may not be used, disclosed, or published without the written consent of Biogen MA Inc.

### 4.3. Additional Information

#### 4.3.1. Site Personnel

A minimum of 3 separate health care professionals (HCPs) are required:

1. A treating HCP (the Principal Investigator [PI] or Sub-investigator may serve as a treating HCP) who is responsible for the following:
  - Administration of Montreal Cognitive Assessment (MOCA) at Day 1, Week 80, and during management of amyloid-related imaging abnormalities (ARIA) cases.
  - Management of routine neurological care of the subject.
  - Assessment (including assignment of causality) and treatment of adverse events (AEs).
  - Review of selected hematology and blood chemistry results from the central laboratory to assess if the subject's study treatment should be temporarily withheld or permanently discontinued according to the criteria detailed in Section 10.1.
2. An independent rating HCP (designated by the PI of the site) who is responsible for administering the Clinical Dementia Rating (CDR)
3. A second independent rating HCP (designated by the PI of the site) who will administer the Alzheimer's Disease Assessment Scale-Cognitive Subscale (13 items) [ADAS-Cog 13], Alzheimer's Disease Cooperative Study-Activities of Daily Living Inventory (Mild Cognitive Impairment version) [ADCS-ADL-MCI], and the Mini-Mental State Examination (MMSE)

The 2 independent rating HCPs must not be involved with any other aspect of subject care and management and must remain blinded to AEs, concomitant therapy, laboratory data, imaging data, or any other data that have the potential of revealing the treatment assignment. The 2 independent rating HCPs must not share any information about subjects. PIs cannot serve as rating HCPs. The treating HCPs must not discuss AEs (e.g., ARIA) with the independent rating HCPs.

To ensure consistency across sites, rating HCPs must complete the standardized study-specific qualification process on clinical efficacy assessment scoring prior to administration of the specific assessment at their site. All sites must attempt to maintain the same rating HCP throughout the study for specific assessments in an attempt to remain consistent. Each subject should have the same rating HCP perform the subject's specific rating assessment throughout the study. A qualified approved back-up rater should only conduct assessments in place of the primary rater due to extenuating circumstances resulting in unavailability (e.g., due to illness, vacation, or travel). If a rating HCP has to be replaced, the new rating HCP must undergo the study-specific qualification process prior to administration of the assessment.

CONFIDENTIAL

The information contained herein may not be used, disclosed, or published without the written consent of Biogen MA Inc.

Hematology and blood chemistry data will be sent to the investigational sites to aid in management of the subject. As with other laboratory and clinical information, these data should NOT be reviewed by the rating HCPs.

The roles of independent raters and treating HCP are NOT interchangeable at the subject level. In addition, the 2 independent raters are not interchangeable at the subject level. If a rater has administered the CDR to a subject, they may not administer the other neurocognitive assessments to that subject at any point during the study.

An unblinded pharmacist (or authorized designee) will be responsible for the storage, distribution, preparation, and accountability of study treatment. The unblinded pharmacist will also be responsible for maintaining the unblinded pharmacy record separate from the main study file in order to support the study blind.

CONFIDENTIAL

The information contained herein may not be used, disclosed, or published without the written consent of Biogen MA Inc.

